#### Aim 3 – Formative evaluation (see Appendix 3 for questionnaires)

Working Alliance Inventory-Short Revised (WAI-SR) is the 12-item short form version of this widely used instrument assesses three key aspects of the therapeutic alliance: (a) agreement on the tasks of therapy, (b) agreement on the goals of therapy and (c) development of confidence, trust, comfort, and acceptance. WAI-SR has good internal consistency (alpha ranges from 0.89-0.92) and convergent validity.

Client Satisfaction Questionnaire (CSQ-8) is an 8-item, self-administered measure of client satisfaction with services. The CSQ-8 is unidimensional, yielding a homogeneous estimate of general satisfaction with services. CSQ-8 has been extensively studied, and while it is not a measure of a client's perceptions of gain from treatment or outcome, it elicits the client's perspective on the value of services received.

## **STATISTICAL ANALYSIS**

Sample size, and power. Our primary aim is to demonstrate that the efficacy of REVAMP management is not clinically inferior to in-person care. Efficacy will be measured as the change in FOSQ-10 score from pretreatment to 3 months following initiation of APAP treatment (Hypothesis 1a). In the recent study by the PI of patients with suspected OSA (N=296) randomized to either home testing or standard in-laboratory testing, mean (SD) functional outcome score improved 1.74 (2.81) in the home group and 1.85 (2.46) in the in-lab group (both  $p<.0001$ ), and improvements in FOSQ in excess of 3 have been reported. Increases less than 1 point are not clinically significant. Assuming that an increase of more than 1 point in mean FOSQ score would indicate an important clinical difference, then the non-inferiority hypotheses for FOSQ score may be expressed:  $H_0: \Delta_R - \Delta_P \leq -1.0$  vs.  $H_a: \Delta_R - \Delta_P > -1.0$  where "R" represents REVAMP management and "P" is in-person management. Assuming a common SD=2.80, 114 patients/group are required to achieve at least 85% power to reject the null hypothesis, i.e., find that the change in FOSQ score among patients receiving the telehealth-based management is > 1 point lower than that in patients assessed in-person.

Using a similar approach to estimate the sample size needed to test non-inferiority of APAP adherence (Hypothesis 1b), mean (SD) PAP use of participants enrolled in our REVAMP pilot study was 5.3 (2.2) hours/day (see Preliminary Results). Based on a non-inferiority delta of -0.75 hr/day and assuming a SD=2.2, the 114

patients/group needed in Aim 1 will achieve an 80% power to reject the Aim 2 null hypothesis, i.e., PAP adherence among patients receiving REVAMP management is  $> 0.75$  hr/day lower than that in patients assessed in person. We note that the projected sample size for Aim 1 is the same as that achieved in our previous study which demonstrated clinical non-inferiority of home vs in-lab testing using the same outcomes.

Based on current referrals to the 3 clinical sleep centers, we anticipate that 20% of subjects enrolled will not have OSA. Adding to this estimate a 20% drop-out rate of patients diagnosed with OSA and initiated on APAP, we need to enroll a total of 356 subjects, i.e., approximately 119 subjects per clinical site. We are confident that we will be able to achieve this goal. Given our clinic and personnel resources, we plan to enroll 6 patients per month per site. We anticipate that it will take about 2 years to enroll the participants (see Gant chart). Thus, we will have at least 9 months of post treatment cost data on all participants for our cost-effectiveness analysis, while the longest will be about 2 years. The longer follow-up should provide the opportunity to observe potential long-term cost benefit and outcome differences between the testing methods.

**Descriptive comparisons at baseline.** Descriptive statistics will be computed for all outcomes; distribution checks will be performed using histograms, quantile plots, and goodness-of-fit tests. Sample characteristics will be summarized using mean (SD) for continuous outcomes and frequency and percent for categorical variables. Descriptive analyses will be performed to characterize the treatment groups separately by clinical center and to confirm that the randomization resulted in no clinically significant treatment group differences at baseline. Partial correlations (controlling for site and group) between baseline factors and outcome measures will be computed to identify potentially important covariates. The primary non-inferiority tests will be repeated, controlling for baseline factors that are found to have both clinically significant treatment group differences and evidence of association with either 1-month or 3-month change in FOSQ score.

**Statistical methods for non-inferiority hypotheses.** Aim 1 will determine if REVAMP management is not clinically inferior to in-person treatment, in terms of the difference between baseline and post-treatment FOSQ score (Hypothesis 1A), and mean APAP use (Hypothesis 1B). To test the Aim 1 hypotheses, we will use a modified intent to treat analysis set, i.e., participants with a diagnosis of OSA who were treated with PAP with or without supplemental oxygen. This strategy will avoid potential bias in the non-inferiority analysis of treatment effect. To demonstrate non-inferiority for Hypothesis 1a we will test the primary non-inferiority hypothesis:  $H_0: \Delta_{R-P} \leq -1$  vs.  $H_a: \Delta_{R-P} > -1$ ; where  $\Delta_R$  and  $\Delta_P$  are the mean FOSQ-10 change scores from baseline to 3 months in the REVAMP (R) and in-person (P) groups, respectively, and where a positive change score indicates improvement. In these equations we have explicitly included the value of the pre-specified non-inferiority margin,  $\delta=1$ , for change in FOSQ score. The hypothesis will be tested by using analyses of covariance to construct least squares estimates of the (adjusted) group differences in mean values along with their 90% confidence intervals (CI). The lower bound of the 90% CI is equivalent to the lower bound of a 95% one-sided non-inferiority CI. If the lower bound exceeds the *a priori* non-inferiority delta, then the null hypotheses of inferiority can be rejected at  $\alpha=0.05$ .

The primary analysis will use mixed effects models for longitudinal data which make use of all available scores for each participant at each measurement time and permit adjustment for inter-group differences that are not balanced through randomization. All analyses of mixed models will account for clinical site. For the change in FOSQ score, baseline FOSQ score will also be included as an *a priori* covariate. Factors that are pre-specified as being possible confounders in the association of treatment assignment and outcome are age, sex and race. We anticipate little confounding from these patient-level factors given the blocked randomization scheme to ensure balance between treatment groups. The site by treatment group interaction will not be included and this decision reflects recommendations that differences among treatment group means should be estimated weighting sites according to the amount of information they provide. With this weighted estimate, each within-center estimate is given a weight based upon its precision. A series of mixed models is proposed; each outcome identified in the aims will be rotated individually in the modeling process. We assume that change outcomes will be normally distributed but will check the distribution of each outcome before modeling, and, if necessary, use a generalized linear mixed model to accommodate alternative distributions.

A similar analysis will be conducted to test Hypothesis 1b:  $H_0: \mu_R - \mu_P \leq -0.75$  hr/night vs.  $H_a: \mu_R - \mu_P > -0.75$  hr/night; where  $\mu_R$  and  $\mu_P$  are the mean APAP hr/night of patients receiving REVAMP (R) versus in-person (P) management. If the lower bound of the 95% one-sided confidence interval exceeds the non-inferiority delta of  $-0.75$  hr/night, then the null hypotheses of inferiority can be rejected at  $\alpha=0.05$ .

**Multiple comparisons.** No adjustment for multiple comparisons will be performed to account for testing of two primary hypotheses, since rejection of both non-inferiority hypotheses are necessary to conclude that at-home assessment is not clinically inferior relative to in-lab assessment.

**Analysis of secondary clinical outcomes in Aim 1.** Secondary outcomes in Aim 1 include changes from baseline to Month 3 in scores of the ESS, SF-12 (physical and mental health components), and CES-D questionnaires. For each secondary outcome, analogous analyses of covariance models will be used to determine least squares adjusted treatment group differences in mean change along with 95% confidence

intervals since non-inferiority deltas are not pre-specified. Baseline values of the outcome measures will be included in their respective ANCOVA models. The above results will be interpreted as hypothesis generating.

**Missing data methods.** The mixed model approach uses information in the covariance matrix of predictors and outcomes over time to implicitly impute missing 3-month FOSQ values. Of note, participants will complete the assessment battery at 1-month following initiation of treatment. Therefore, subjects missing month 3 results will not be excluded. These imputations are valid if the likelihood of missingness is independent of treatment group, conditional on observed data included in the model, i.e., if missing data are missing at random (MAR). For comparison with earlier studies, we will also perform the analyses using the last observation carried forward method. Finally, in sensitivity analyses, we will evaluate the impact of departure from the assumed MAR mechanism by using multiple imputation (MI) to implement a selection model approach. In this way, we will be able to compare estimated effects based on different assumptions about the missingness mechanism, and to assess the sensitivity of our estimates to these assumptions. If data on predictors is incomplete, we will use multiple imputation methods (as implemented in SAS PROC MI and MIANALYZE) to generate multiple imputed complete datasets, perform analyses, and then combine analysis results to produce estimates that are asymptotically unbiased, with standard errors that account for imputation uncertainty.

**Modified intent-to-treat and per-protocol populations.** Primary analysis for non-inferiority will be based on all randomized participants initiated on APAP with at least one FOSQ follow-up score. In a secondary analysis, the non-inferiority test will be repeated using a per protocol cohort (patients who have been initiated on APAP and have non-missing endpoints at month 3), since protocol violations can add noise making it more difficult to distinguish between the two active treatment groups.

**Statistical methods for Aim 2.** Aim 2 will determine if REVAMP management of patients with OSA is cost-effective compared with in-person care. The perspective of the analysis will be that of the VA. While the VA has the general well-being of veterans as its goal, we will focus our attention on health care costs, in part because VHA patients with OSA are older and less likely to work. The analyses for Aim 2 will be based on all randomized participants, as this is the target population for the evaluation of Aim 2 and Aim 3 outcomes related to management of this patient population. We will perform a secondary analysis using the modified intention to treat sample (Aim 1 analysis set). The primary outcome measure in Aim 2 will be the difference in sleep-related cost between the two delivery modalities. Our hypothesis is 2a)  $H_0: \Delta C = 0$  vs  $H_A: \Delta C < 0$ . Based on data from our prior study of home vs in-lab diagnosis, we assume average 3-month sleep-related costs of \$1755 (SD, 745) for the home group and of \$2538 (SD, 1065) for the in-lab group. Resulting power is 1.0 for sample size of 114 per group and remains greater than 0.9 if, when including participants without OSA on HST and participants with CSA/CSR, the means are reduced by 25% and the SDs are increased by 25%.

Secondary outcome measures include the difference in total costs, the difference in QALYs, and the ratios of the differences in cost and QALYs. The secondary hypothesis for the cost-effectiveness ratio is 2b)  $H_0: \Delta C/\Delta Q > 100,000$  vs  $H_A: \Delta C/\Delta Q \leq 100,000$ . As with the efficacy and non-inferiority analyses, the cost difference ( $\Delta C$ ) and the preference score difference ( $\Delta Q$ ) will be estimated using mixed effect models for longitudinal data. QALYs will be constructed by taking the area under the quality-adjusted survival curve. The cost-effectiveness ratio ( $\Delta C/\Delta Q$ ) will be calculated by dividing the estimated difference in cost by the estimated difference in QALYs. Confidence intervals for the cost-effectiveness ratios will be calculated using Fieller's theorem method. A point estimate less than 100,000/QALY and a 90% confidence interval that excludes \$100,000 will be evidence that we can reject the null hypothesis that the incremental cost-effectiveness ratio is not less than \$100,000.

Costs, QALYs, and cost-effectiveness ratios will be calculated for costs and effects during the first 3 months following initiation of APAP treatment and for the full period of follow-up (maximum, 2 years). The study design (follow-up extending from enrollment until 3 months after last patient is enrolled) introduces substantial administrative censoring that – as with the primary analysis – will be addressed by use of a mixed model approach (i.e., patients will have different lengths of follow-up, and thus different costs and QALYs, simply because they were enrolled at different times). Because this censoring is due primarily to administrative reasons, it is generally considered to yield data that are missing completely at random (MCAR). While use of the electronic medical records for the collection of cost data will lead to limited missing cost data, there may be censoring of cost data for services outside the VHA and of the QALY measures due to loss to follow-up. If such drop-out is related to disease severity or to outcomes after randomization, it generally would be considered to yield data that are either missing at random (MAR) or that are non-ignorably missing.

**Statistical methods for Aim 3, Quantitative component.** Aim 3 will compare patient-centered treatment acceptability and process measures of the two management approaches. We will evaluate patient acceptance of telemedicine-based care by comparing the between-group differences in attrition, therapeutic alliance, and satisfaction with care. The primary quantitative objective outcome measure in Aim 3 will be percent of patients who drop out of each treatment. The primary subjective outcome measures will be change in the WAI-SR and CSQ-8 scores. For this exploratory aim we will estimate mean values and confidence intervals. Mixed effects models will be used to estimate the between-groups difference in means and confidence intervals, for each of

the outcome measures. Results will be ascertained via ITT and per-protocol procedures as previously discussed. A series of mixed models is proposed for each outcome identified in Aim 3 (WAI-SR, CSQ-8).

Qualitative data analysis. Interviews will be digitally recorded with the participant's permission, transcribed by a professional transcriptionist, and prepared as primary documents to be loaded into Atlas.ti software for data management and analysis. Atlas.ti is a software program designed to assist in the management and analysis of qualitative data, including primary documents (e.g., transcripts), secondary notes (e.g., memos written by the investigators concerning methodological issues), and analytical notes (e.g., emerging theories to be tested through further data collection and analysis). Atlas is particularly suited to the constant comparative method most closely associated with grounded theory, adapted for use in healthcare and health services research. Analysis of patient interviews will be guided by Aim 3: to identify patient perspectives, attitudes, and preferences regarding REVAMP versus in-person management of patients with OSA, as well as barriers and facilitators to participation in either clinical pathway. *Similarly, analysis of provider interviews will focus on identifying providers' attitudes and perspectives on acceptability of delivering care via REVAMP vs. in-person, and perceived barriers and facilitators to implementation, spread, and maintenance of REVAMP as a means to deliver treatment for patients with OSA.*

Analysis will follow a series of systematic steps in order to provide a structured approach to ground the flexible, exploratory nature of qualitative research and ensure transparency of the process for examination by other researchers in the field. An initial set of codes for each type of interview data (e.g., patient, provider) will be developed and defined after reviewing the first few transcripts for each type of interview (open coding). The codes will be revised and refined through discussion involving research team members. Any disagreements in coding will be resolved through discussion with the research team and once the final coding scheme is standardized, all transcripts will be coded by a research assistant overseen by [name]. Examination of coded text across transcripts and relationships between codes (axial coding) will identify recurrent themes and categories related to Aim 3. Separate codebooks will be developed for coding of each type of interview data (*patient, provider*), but analysis and summary of data will consider themes that emerge within each group (e.g. patient-specific themes, provider-specific themes), as well as themes that emerge across both groups.

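### The supportive repeat of the non-inferiority tests picks its covariates from the observed data, and screens those for APAP adherence (1b) on FOSQ change instead of on adherence

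*Combined protocol and SAP*

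**What the plan says.** All of this is in the combined protocol and SAP, under STATISTICAL ANALYSIS.

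- **Descriptive comparisons at baseline.** A general screen comes first: "Partial correlations (controlling for site and group) between baseline factors and outcome measures will be computed to identify potentially important covariates". Then comes the adjustment rule: "The primary non-inferiority tests will be repeated". The repeat is made "controlling for baseline factors that are found to have both clinically significant treatment group differences and evidence of association with either 1-month or 3-month", and the second condition reads in full "association with either 1-month or 3-month change in FOSQ score". Neither condition has a threshold, and no candidate list is attached.
- **Multiple comparisons.** There are two primary tests, FOSQ-10 change (1a) and APAP hours (1b), and both must succeed: "No adjustment for multiple comparisons will be performed to account for testing of two primary hypotheses".
- **Statistical methods for non-inferiority hypotheses.** "All analyses of mixed models will account for clinical site", and baseline FOSQ is an a priori covariate for FOSQ change. On other factors the text says: "Factors that are pre-specified as being possible confounders in the association of treatment assignment and outcome are age, sex and race". It does not say that these three enter the model. It continues: "We anticipate little confounding from these patient-level factors given the blocked randomization scheme to ensure balance between treatment groups". The same paragraph notes that the mixed models allow adjustment for imbalances left by randomization, without naming any. Test 1b is described only as analysed in a similar way, with no covariates of its own.
- **Participant randomization** (under RESEARCH DESIGN AND METHODS). Allocation is in blocks of six within site, three to each arm. No patient factor is used for stratification.

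**The concern.** The covariate set of the repeated tests depends on two looks at the data: how the arms happened to differ, and which factors turned out to correlate with FOSQ change. With no thresholds, two competent analysts could fit different models and both follow the plan.

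For 1b the difficulty is more specific. A covariate matters to a comparison of APAP hours if it is imbalanced and predicts APAP hours. The rule asks whether it predicts FOSQ change. A factor that drives adherence but not FOSQ change fails the screen however imbalanced it is, and a factor that predicts only FOSQ change is admitted to no purpose. Non-inferiority needs both 1a and 1b, so a check on 1b that looks in the wrong place gives little reassurance about half of the claim.

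The statement that blocking will balance age, sex and race adds unearned confidence that such a check will rarely be needed.

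**Working it through.** **The plan's own figures.** Inputs from the sample-size text: 114 per group, one-sided alpha 0.05, true difference 0; 1a margin 1.0 and SD 2.80; 1b margin 0.75 and SD 2.2. The standard error factor is sqrt(2/114) = 0.1325.

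- 1a: n = 2 × 2.80² × (1.645 + 1.036)² / 1.0² = 112.7, so 113 per group. Power at 114 is Phi(1.0/(2.80 × 0.1325) − 1.645) = 85.3% (85.2% by the t distribution). The plan's 114 for at least 85% is reproduced.
- 1b: Phi(0.75/(2.2 × 0.1325) − 1.645) = 82.4% (82.2% by t), against a stated 80%. The plan is slightly conservative.
- Total: 228/0.8/0.8 = 356.25, against 356.

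None of these figures is in dispute.

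**Does blocking balance patient factors?** It fixes the numbers per arm within site and nothing else. For one continuous factor at 114 per arm, P(|standardized difference| > c) = 2 × [1 − Phi(c/0.1325)]. The cut c is an assumption, since the plan gives none.

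| Cut c | One factor | At least one of 3 | At least one of 15 |
|---|---|---|---|
| 0.2 SD | 13.1% | 34% | 88% |
| 0.3 SD | 2.4% | 7% | 30% |

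The last two columns assume independent factors: 1 − (1 − p)^k. With a common correlation of 0.5, the 88% falls to about 70%. These are the chances that simple randomization would give; blocking does not reduce them.

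**What the FOSQ screen does to 1b.** This is a simulation on assumed inputs: 15 independent baseline factors, two of them correlated 0.3 with APAP hours, imbalance cut 0.2 SD, association at p < 0.05, 4,000 to 6,000 runs per scenario.

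- At least one adherence predictor is imbalanced in 1 − (1 − 0.131)² = 24% of trials (simulated 24 to 25%).
- If those predictors are unrelated to FOSQ change, the FOSQ screen picks one up in 4 to 6% of those trials and an adherence screen in over 99%. The mean shift left in the estimate, in the direction of the imbalance, is 0.157 to 0.173 hr, or 21 to 23% of the 0.75 hr margin. With an adherence screen it is 0 to 0.01 hr.
- Check by hand: the mean |difference| given that it exceeds 0.2 SD is 0.1325 × phi(1.51)/[1 − Phi(1.51)] = 0.258. Then 0.3 × 2.2 × 0.258 = 0.170 hr, which agrees.
- If they correlate 0.1 with FOSQ change, the FOSQ screen picks one up in 32% of those trials and leaves 0.128 hr (17% of the margin).

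**Type I error for 1b at the margin** (nominal 5%, Monte Carlo standard error about 0.3 points): unadjusted 4.8 to 5.2%; FOSQ-screened 4.8 to 5.0%; adherence-screened 4.1 to 4.5%. If success could be claimed when either the unadjusted or the FOSQ-screened test passes, 5.0 to 5.5%. A similar simulation of the rule for 1a gave 3.9 to 4.7%, or 5.5 to 5.8% if either result counted.

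**The case against.** The strongest reply is that the rule governs a repeat of the primary tests and not the tests themselves. The primary model for 1a already fixes site and baseline FOSQ, and it names age, sex and race in advance. Nothing in the plan lets the repeat override the primary result. This stands, and it limits the point to a supportive analysis. A reader might infer that the primary tests lack pre-specified covariates, or that their conclusion is compromised; the text supports neither.

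A reader might also infer an inflated false-positive rate. The simulations do not show one: the rule itself runs at or slightly below 5%. The small excess appears only if either result may be used to claim success, and the plan does not say that.

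A third tempting reading is that a fixed list would clearly raise power. For 1a, simulation gave 88 to 93% for a fixed list, 86 to 88% for the plan's rule and 85 to 86% unadjusted. But the fixed list was handed every prognostic factor by construction, at assumed correlations of 0.2 to 0.3, and the plan's primary model is not unadjusted. If baseline FOSQ is one of those factors, the plan already starts at 87 to 88%. The documents give no correlations, so no gain can be claimed.

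On 1b, it can be said that the plural may be loose drafting and that the preceding sentence screens against outcome measures in general. A drafting slip is quite possible. Still, the plan names two primary tests, the rule applies to the tests in the plural, and its only association criterion is FOSQ change. An analyst following the text would screen 1b on FOSQ.

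Finally, the blocking sentence states an expectation and changes no analysis. That is true, and randomization does balance these factors on average; but the reason given for the expectation is wrong.

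**Conclusion.** The point holds for the supportive repeat. Its covariates are chosen from observed imbalance and observed outcome association with no thresholds, and for 1b the association is with the wrong outcome. An imbalanced predictor of adherence can therefore be missed. On the assumed inputs this leaves about 0.13 to 0.17 hr in the affected trials, roughly a quarter of all trials. That size rests on correlations of 0.3 with APAP hours and 0 to 0.1 with FOSQ change, and on a 0.2 SD cut; none of these is in the documents. The imbalance can favour either arm, so the shift averages out over repeated trials; it matters for reading one trial's result.

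Two smaller points go with it. Naming age, sex and race as possible confounders leaves open whether they are in the model. The claim that blocking balances them is incorrect. Type I error is not materially affected, and the sample size is not in question. The change is worth making because the discretion is unnecessary and the remedy is cheap.

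**What to change.** Replace the selection rule under Descriptive comparisons at baseline with a covariate list for each outcome. Fix the lists before outcome data are examined; a deadline tied to unblinding would not fit, because the plan says research personnel cannot be blinded to assignment. Use variables already collected at baseline:

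- **1a:** site, baseline FOSQ-10, age, sex, race, and any other named prognostic factors, such as baseline ESS or CES-D.
- **1b:** site, age, sex, race, and named expected predictors of adherence. A list copied from 1a should not be assumed to suit this outcome.

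Fit each list whatever the observed balance, and state plainly that these terms are in the model.

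If an imbalance-driven repeat is kept, label it a sensitivity analysis that cannot override the primary result, define both thresholds, and screen 1b on association with APAP hours. Delete the statement that blocking balances age, sex and race.

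Cost: SAP wording and a few degrees of freedom out of about 228 participants. The 114 per group and 356 in total do not change.
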